| 
Statistical Analysis
 | 
The aim of the statistical analysis will be to prove the efficacy and safety of LRG-002 (Lactobacillus rhamnosus GG not less than <math>2 \times 10^{10}</math> CFU) to be superior to placebo in antibiotic-treated patients with acute respiratory diseases, as an adjunct treatment for prophylaxis of antibiotic-associated diarrhea (AAD).
 
The analysis will be performed for comparison of:
 
 
- LRG-002 and matching placebo.
 
 
The primary efficacy endpoint will be analyzed with a logistic regression model with fixed factors for treatment group and age group.
 
The primary efficacy endpoint will be considered achieved if the odds ratio for the occurrence of AAD between placebo and LRG-002 is significantly higher than 1 (i.e. the occurrence of AAD is lower in the LRG-002 group).
 
The secondary parameters will be compared with the following method:
 
 
- continuous variables will be compared by Mann—Whitney-Wilcoxon test.
 
 
Binary and ordinal variables will be compared by chi- square test or Fisher's exact test (depending on the number of expected observations per cell: <math><5</math> or <math>\geq 5</math>).
 
The analysis of study subjects with AE (SAE) will be performed with chi-square test or Fisher's exact test.
 
Poisson regression will be used for analysis of AE (SAE) frequency. The significance level is assumed as <math>p < \alpha</math>, with <math>\alpha = 0.05</math>.
 
Sample size calculation
 
Primary endpoint is the frequency of occurrence of AAD from the
 |

first to the last day of LRG-002 administration compared with placebo in antibiotic-treated patients with ARDs.

A test based on odd ratio was used to calculate sample size.

The following parameters were obtained from Figure 2 in a meta-analysis [1] using only data for AAD:

Using only data for AAD studies in adults from the cited publication, the rate for the control group is 0.24 and for the treatment group 0.14.

Using only data for LGG studies in adults and children, the rate for the control group is 0.26 and for the treatment group 0.15.

In meta-analysis [14] figures from Table 1 demonstrate a rate of 0.196 for a treatment group and 0.29 for a placebo group (only trials for adults with LGG were taken into consideration).

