### **9.2 Methods and timing for evaluating, recording and analyzing safety parameters**

Safety parameters are evaluated at each visit planned in this study, as well as at unscheduled visits.

Safety evaluation will be based on the following parameters (between Visits 1 and 3), compared between the investigational medicinal product and placebo:

Frequency of adverse events (AEs) and/or serious adverse events (SAEs) in the treatment groups, including:

- Overall AE rate as compared to placebo;
- Frequency of AEs according to the results of physical examinations during each visit compared

with placebo;

- AE incidence according to the results of the vital signs assessment (HR, BP, BT, RR) at each visit compared with placebo;
- AE incidence according to the ECG results on Day 15 ( $\pm 2$ ) compared with placebo;
- AEs incidence according to the results of laboratory examinations on Days 7( $\pm 2$ ) and 15( $\pm 2$ ) compared with placebo;
- Frequency of AEs according to the everyday patients' records of well-being self-evaluation in the diary.

Diary records will be reviewed by the Investigator. In case the researcher considers that the records in the diary meet criteria of AE, the patient will be questioned about this event, and all information (including an evaluation of causality) will be documented.

Adverse event will be described according to the following scheme:

- Description of adverse event;
- Seriousness of adverse event (compliance with seriousness criteria);
- severity;
- duration;
- causal relationship with the investigational product;
- actions taken in relation to the study drug;
- actions taken in relation to the patient;
- outcome.

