Patient complaints based on the results of the daily records of well-being self-assessment in the diary will be summarized into groups, and comparison between groups shall be made using appropriate tests for quantitative and qualitative data. Gastrointestinal AEs (determined using standardized MedDRA requests for the corresponding symptoms), regarded by the Investigator as associated with the study therapy, will be analyzed separately. Descriptive statistics methods will be used for the results. Comparison of the incidence of new AEs in the study groups will be carried out using the Fisher's exact test or the chi-square criterion, depending on the number of prospective observations in one cell ( $<5$  or  $\geq 5$ ); the comparison of severity degree (and possible causal relationship between received medicinal product and AE) will be carried out using the Cochran – Armitage test for linear trends for ordered categorical data.

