### **10.7 Procedures for reporting any deviations from the original statistical plan**

All deviations from the original statistical plan should be described and justified in an amendment to the protocol and / or the final study report (in the latter case, the statistical analysis plan developed prior to the initiation of the final statistical analysis should contain a list of these deviations with justification of reasons for deviating from statistical plan according to the Protocol).

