8.1. Adverse events

Safety assessment will also be based on the following parameters (between Visits 1 and 3) compared between the investigational medicinal product and placebo:

Incidence of adverse events (AEs) and/or serious adverse events (SAEs) in the treatment groups including:

- Overall AE rate as compared to placebo;
- AE rate according to the results of physical examinations during each visit compared with placebo;
- AE incidence according to the assessment of the vital signs (HR, BP, BT, RR) at each visit as compared to placebo;
- AE incidence according to the ECG results on Day 15 (± 2) in comparison with placebo;
- AE incidence according to the results of laboratory examinations on Days 7 (± 2) and 15 (± 2) as compared to placebo;
- AE incidence according to the results of daily self-examination of the state of health recorded in Self-Observation Diary.

The study doctor will review the entries in the Self-Observation Diary. If the study doctor believes that the information in the Diary complies with the AE criteria, they will ask the patient about this event and document all information about the AE (including the causality assessment).

The AEs will be described according to the scheme given below:

- AE description
- Severity of the adverse event (meeting the severity criteria)
- AE severity
- AE duration
- Relation to the IMP
- Measures taken in relation to the investigational medicinal product
- Measures taken in relation to the patient

- **Outcome**

Adverse events will be coded according to the MedDRA

Methods of descriptive statistics will be used to represent the results. A comparison of the incidence of new AE cases in the study groups will be performed using the Fisher's exact test or the chi-square test, depending on the number of proposed observations in one cell (< 5 or ≥ 5), and a comparison of the severity (and the possible causality between the administered medicinal product and AE) will be conducted using the Cochran–Armitage test for linear trends for ordered categorical data.

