Appendix 1. Table layouts

Table No. 1. Example of a statistical table for a quantitative variable

Visit	Group	Parameter	Variable name
Visit number	Group 1	N	
		Missed	
		Mean	
		95% CI	
		SD	
		Median	
		Min	
		Max	
		Q1	
		Q3	
	IQR		
	Group 2	N	
		Missed	

STATISTICAL ANALYSIS PLAN

Visit	Group	Parameter	Variable name
		Mean	
		95% CI	
		SD	
		Median	
		Min	
		Max	
		Q1	
		Q3	
		IQR	

Table No. 2. Example of a group comparison table for a quantitative variable

Visit	No.	No.	No.	No.
Variable	variable name			

STATISTICAL ANALYSIS PLAN

Shapiro–Wilk test, p-value	Group 1				
	Group 2				
Student's t-test, p-value					
Mann–Whitney test, p-value					

Table No. 3. Example of a repeated comparison table for a quantitative variable

Variable	Group	Visit	Friedman test/ ANOVA for repeated measurements	Wilcoxon test/ Student's t-test for repeated measurements
variable name	Group 1	Comparison of visits		
		No. vs. No.		

STATISTICAL ANALYSIS PLAN

Variable	Group	Visit	Friedman test/ ANOVA for repeated measurements	Wilcoxon test/ Student's t-test for repeated measurements
		No. vs. No.		
		No. vs. No.		
		No. vs. No.		
		No. vs. No.		
		No. vs. No.		
	Group 2	Comparison of visits		
		No. vs. No.		
		No. vs. No.		
		No. vs. No.		
		No. vs. No.		

STATISTICAL ANALYSIS PLAN

Variable	Group	Visit	Friedman test/ ANOVA for repeated measurements	Wilcoxon test/ Student's t-test for repeated measurements
		No. vs. No.		
		No. vs. No.		

Table No. 4. Example of a statistical table for a categorical variable

Variable	Visit	Group	Variable value	Amount	% by group	% by groups for visit	Fisher's test, p-value
variable name	No.	Group 1	value				
			value				
		Group 2	value				
			value				

STATISTICAL ANALYSIS PLAN

Table No. 5. Example of a table of adverse events for calculating the number of all adverse events

Adverse events	Group	Amount	% of the number of AEs in the group	% of the total number of AEs	Binomial test, p-value
All adverse events	Group 1				
	Group 2				
SOC	Group 1				
	Group 2				
PT	Group 1				
	Group 2				

Table No. 6. Example of a table of adverse events for calculating the number of adverse events in the context

Adverse events	Group	variable name	Amount	% of the number of AEs in the group	% of the total number of AEs	Fisher's test, p-value
	Group 1	value				
		value				

STATISTICAL ANALYSIS PLAN

Adverse events	Group	Variable name	Amount	% of the number of AEs in the group	% of the total number of AEs	Fisher's test, p-value

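### AE frequency has three different planned tests, and the two that count events treat repeated AEs in one patient as independent

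*Protocol*

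**What the plan says.** The methods for AE frequency, by place:

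- **Protocol Synopsis, Statistical Analysis.** Patients with an AE get one test: "The analysis of study subjects with AE (SAE) will be performed with chi-square test or Fisher's exact test". The next sentence adds another: "Poisson regression will be used for analysis of AE (SAE) frequency". Because patients with AEs already have their own test, the Poisson model reads as a separate comparison of event counts. The 0.05 significance level follows directly. No dispersion parameter, robust variance, exposure offset or covariate is mentioned.
- **Protocol 10.1.4.** "Comparison of the incidence of new AEs in the study groups will be carried out using the Fisher's exact test or the chi-square criterion", with Cochran–Armitage for severity and causality. Poisson regression is not mentioned.
- **SAP 8.1.** Nearly the same text as 10.1.4: "comparison of the incidence of new AE cases in the study groups will be performed using the Fisher's exact test" or chi-square. Again there is no Poisson regression.
- **SAP Appendix 1, Table 5.** The layout for the number of all AEs has a column headed "Binomial test, p-value". Its percentages are of AEs in the group and of AEs overall, not of patients. Table 6 uses the same AE-based percentages beside a Fisher p-value.

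On changes to the plan, protocol 10.7 says: "All deviations from the original statistical plan should be described and justified". The SAP text available contains no entry about the Synopsis model.

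**The concern.** A statistician programming the safety tables would find three answers to one question and no statement of whether the unit is the patient or the event.

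The unit matters. A Poisson model without a dispersion adjustment sets the variance of the AE count equal to its mean. A binomial test on the split of AEs between arms makes the same assumption after conditioning on the total. Both take a patient's second and third AE to be as informative as first AEs in two other patients. If some patients contribute several AEs and many contribute none, the variance exceeds the mean and both tests reject too often. The result could be a spurious safety advantage or a spurious alarm, in a trial whose Synopsis states the aim of showing superior safety as well as efficacy.

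Follow-up can also differ between patients. The plan allows for 20% withdrawal, and a clinically significant AE is itself a listed reason to stop participation (protocol 6.3.1), yet no exposure time enters the count comparison.

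**Working it through.** **What the plan's figures cover.** The documents give no AE rate, dispersion or AE power, so there is no AE figure to reproduce. The stated sample size concerns AAD only: (1.960 + 0.842)² × (0.15×0.85 + 0.26×0.74) / 0.11² = 7.849 × 0.3199 / 0.0121 = 207.5, hence 208 per arm, and 208/0.80 = 260. It reproduces and is untouched by this point.

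**Poisson.** Let φ be the variance-to-mean ratio of AEs per patient. For total counts A and B in equal arms, the naive standard error of the log rate ratio is √(1/A + 1/B), while the true one is √φ times that. Hence

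- true two-sided size = 2 × [1 − Φ(1.96/√φ)];
- naive interval width = 1/√φ of the correct width.

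**Binomial.** With independent events and no difference between arms, A given A + B is binomial with probability 1/2 (assuming a 1:1 null, which Table 5 does not state). With clustering, (A − B)/√(A + B) has variance φ instead of 1, so the same inflation applies.

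**Simulation check.** Negative binomial counts with the same distribution in both arms. Poisson: 208 and 260 per arm, means of 0.5, 1.0 and 3.13 AEs per patient, 40,000 runs each. Binomial: 260 per arm, mean 1, 8,000 runs.

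| φ (assumed) | Poisson size, formula | Poisson size, simulated | 95% interval coverage | Width vs correct | Binomial size, simulated |
|---|---|---|---|---|---|
| 1 | 0.050 | 0.048–0.050 | 95% | 1.00 | 0.045 |
| 1.5 | 0.110 | 0.108–0.111 | 89% | 0.82 | 0.099 |
| 2 | 0.166 | 0.161–0.166 | 83% | 0.71 | 0.160 |
| 3 | 0.258 | 0.252–0.259 | 74% | 0.58 | 0.239 |

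Scaling the standard error by the true √φ brought the simulated Poisson size back to 0.046–0.051. In practice a robust variance or negative binomial model would estimate that factor from the data.

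**Can φ be learned from the documents?** The only per-person AE data are from the open-label study in healthy elderly volunteers (protocol 3.3.2.1): 47 AEs in 15 people, range 1 to 7, mean 47/15 = 3.13. The individual counts are not given, so only bounds follow.

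- Smallest variance: one person with 1, one with 7, thirteen with 3. Variance 1.41, φ = 1.41/3.13 = 0.45.
- Largest variance: nine with 1, five with 7, one with 3. Variance 8.27, φ = 8.27/3.13 = 2.64.

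That interval includes under- and overdispersion, so it does not settle the matter.

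**The case against.** **The Poisson sentence may not be operative.** It occurs once, in the Synopsis. Section 10.1 leaves the complete analysis to the SAP, and 10.1.4 and SAP 8.1 agree on Fisher or chi-square. A reader might infer from the Synopsis that ordinary Poisson regression is the plan's AE analysis and will decide the safety conclusion. The documents do not support that: the same Synopsis plans a patient-level test, and it says nothing either way about how the Poisson variance is to be estimated. This part of the objection stands. It does not remove the point, because Table 5 of the SAP itself tests event counts and shares the weakness.

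**Clustering is plausible but undocumented.** A reader might build a dispersion figure by supposing that each patient with AAD (about 20% on the planning rates of 0.26 and 0.15) adds several gastrointestinal AEs. The documents give neither a background AE rate nor an excess per AAD patient. Diary lines do not become AEs automatically: protocol 9.2 makes it conditional, "In case the researcher considers that the records in the diary meet criteria of AE", after which the patient is questioned. The diary symptoms are also analysed separately as a secondary efficacy endpoint. Moreover, if AAD drove AE counts and the arms differed in AAD as planned, a rejection would reflect a real difference rather than a false one.

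**The deviation argument has limits.** A reader might infer that the SAP dropped the Poisson model in breach of 10.7, so that it remains in force. The SAP follows 10.1.4, which already lacks the model. The conflict begins inside the protocol, between the Synopsis and section 10. What stands is that nothing on record resolves it.

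**Exposure is a small matter.** Participation lasts at most 17 days, and nothing indicates that follow-up will differ by arm. The offset is good practice rather than a correction of a demonstrated bias.

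**Conclusion.** The point holds as an inconsistency with a conditional statistical consequence. Three methods are named for AE frequency, the unit of analysis is not fixed, and the two event-count methods do not allow for repeated AEs in a patient.

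If AEs cluster, the true size of a nominal 5% test is about 11% to 26% for Poisson and 10% to 24% for the binomial test, at variance-to-mean ratios of 1.5 to 3. That range is an assumption. At a ratio of 1 there is no inflation, and the documents cannot show where this trial will lie. The figures also assume that the Poisson model is run without a dispersion or robust adjustment, since none is stated.

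Only safety comparisons of event counts are affected. The primary logistic regression, the sample size and Fisher or chi-square tests that count each patient once are not. This is a minor, inexpensive improvement, not a threat to the trial's main conclusion.

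**What to change.** 1. Keep Fisher/chi-square as the incidence comparison, define it as patients with at least one AE, and give patient denominators in the tables.
2. For any comparison of event counts, replace both the Synopsis Poisson model and the Table 5 binomial test with one method: Poisson regression with robust (sandwich) variance, or negative binomial regression. Include treatment and age stratum as factors and log days on study as offset.
3. Use the same wording in the Synopsis, 10.1.4, SAP 8.1 and Table 5. Alternatively, drop event-count testing and record that deviation, with its reason, under protocol 10.7.

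The cost is a few lines in each document, a revised table layout and a different R call. Intervals widen when AEs cluster, by a factor of √φ: about 1.22, 1.41 and 1.73 times at ratios of 1.5, 2 and 3. If counts are not overdispersed, little is lost.

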| Blinding,
Randomization | 
It will be a double-blind, randomized study.
 
Patients will be included by applying stratified randomization in two strata:
 

• Age < 50 years;

• Age ≥ 50 years.

 
Each treatment group will be balanced at a ratio of 1:1 within each stratum.
 
Stratified randomization is a two-stage procedure in which patients who enter a clinical trial are first grouped into strata. Within each stratum, patients are then assigned to a treatment according to separate randomization schedules. Randomization module of EDC system assigns patient unique randomization code base on group of treatment and stratum. Randomization schedules will be hidden from medical personnel and all other persons involved in the study (monitors, data management, biometry, sponsor etc.), except the specialists responsible for labeling of the IMP and emergency unblinding.
 |

**2. General information**

**2.1 Protocol title, identification number and date**

**Title:** Multicentre, double-blind, randomized, placebo-controlled, parallel-group efficacy and safety study of LRG-002 hard capsules (Lek d.d., Slovenia) used in the prophylaxis of antibiotic-associated diarrhea in adults.

**Identification number:** CT\_002\_LRG\_CAP

**Protocol version:** 3.0

**Date:** June 23, 2020

### 3. Rationale of the study and the program of clinical trials of the medicinal product

#### 3.1 Program of clinical trials of the medicinal product

In accordance with the clinical development program of the LRG-002 medicinal product, capsules (Lek. d.d., Slovenia), Sandoz is planning to perform the clinical trial on the territory of the Russian Federation:

Multicentre, double-blind, randomized, placebo-controlled, parallel-group efficacy and safety study of LRG-002, capsules (Lek d.d., Slovenia) used in the prophylaxis of antibiotic-associated diarrhea in adults. According to Federal Law No. 61-Φ3 (FZ) as of April 12, 2010 On Circulation of Medicines (as amended), the clinical trial with participation of Russia is required for medicinal product authorization on the territory of the RF. Therefore, this clinical trial is designed to investigate LRG-002 tested medicinal product efficacy and safety, capsules as compared with LRG-002 placebo, for prophylaxis of antibiotic-associated diarrhea (AAD) in patients with acute respiratory diseases (ARDs) receiving a standard antimicrobial therapy.

According to the results of the present clinical trial Sandoz is planning to have the LRG-002, capsules medicinal product, authorized.

##### 3.1.1 Investigational drug

**Name of the medicinal product:** LRG-002, capsules.

**Manufacturer:** Lek d.d., [name].

**Dosage form, dosage:** capsules

**Description:** Each capsule contains live lyophilized probiotic bacteria of Lactobacillus genus.

**Composition per 1 capsule:** each capsule contains at least  $1 \times 10^{10}$  CFU of Lactobacillus rhamnosus GG as a lyophilizate.

Excipients: sucrose, maltodextrin, silicon dioxide, magnesium stearate, sodium ascorbate

Capsule shell: hypromellose, titanium dioxide (E171), gellan gum, water.

**Pharmacotherapeutic group:** anti-diarrhea microorganisms, lactic acid producing microorganisms.

**ATC code:** A07FA01

**Pharmacodynamic properties**

Lactobacillus rhamnosus GG comprised in LRG-002 is a well-known probiotic strain and a well-established probiotic bacterium which reconstitutes and maintains the reconciliation of gut microbiota in adults and children.

Along with other bacteria, Lactobacteria (benefit bacteria) are commonly present in human gut microbiota. These bacteria maintain the structure of intestinal cells and their contacts, healthy acid-alkaline reconciliation necessary for normal functioning of digestive enzymes, prevent harmful bacteria overgrowth, influence the intestinal motility (peristalsis) and stimulate the immune system.

Disturbance of the gut microbiota reconciliation (e. g. in viral and bacterial gastrointestinal infections, in therapy with wide spectrum antibiotics and chemotherapy drugs, in irradiation of abdominal and pelvic organs, and when travelling abroad) may cause digestion disorders (such as flatulence, diarrhea and constipation).

The use of Lactobacillus rhamnosus GG positively influences the reconstitution and control of physiologic balance of intestinal microbiota. A wide range of research literature and clinical trials of Lactobacillus rhamnosus GG indicate that this probiotic strain can positively affect gastrointestinal and immune functions. Furthermore, its safety and good tolerability have been demonstrated.

### **Pharmacokinetic properties**

Probiotic bacteria as well as Lactobacillus rhamnosus GG provide a local effect on the gastrointestinal tract. There is no systemic absorption with oral administration. Routine pharmacokinetic studies are thus not applicable. The resistance of Lactobacillus rhamnosus GG to gastric acid and bile allows most of these bacteria to survive during the passage of stomach and duodenum. Bacteria adhere to the intestinal mucous membrane. Like all other microorganisms contained in the gastrointestinal tract, they are gradually excreted by peristalsis and defecation.

